**REPUBLIC OF TURKEY**  
**ISTANBUL UNIVERSITY INSTITUTE of HALTH SCIENCES**  
**DEPARTMENT OF ORAL AND MAXILLOFACIAL RADIOLOGY**

**RESEARCH PROTOCOL**

**Number of Protocol: 2019/73**

**Date: 09/09/2019**

NAME OF THE RESEARCH	Investigation of the Reliability of Ultrasonography Usage in the Diagnosis of Temporomandibular Joint Diseases: A Prospective Study
-----------------------------	---

RESOURCES OF THE RESEARCH AND RATIONALE	
Today, a significant increase in the prevalence of temporomandibular joint diseases is observed. In addition to the basic clinical examination, there are several methods and techniques for the diagnosis of temporomandibular joint diseases. Magnetic resonance imaging is considered the gold standard in the evaluation of the articular disc as well as soft tissues. Computed tomography is used to diagnose bone lesions such as bone erosion, fractures, postoperative deformities, and deformities of the adjacent temporal bone. All of these methods have limitations. Ultrasound imaging of the joints and surrounding soft tissues is an alternative method for the diagnosis of temporomandibular joint diseases(1). However, the use of ultrasonography in the diagnosis of temporomandibular joint diseases is rare, but although there are several reports suggested in the literature, it is less expensive, less time consuming and easy to apply than other conventional imaging tools such as magnetic resonance imaging, arthrography and computed tomography scanning. recently gained attention and importance in terms of both research and patient care(2,3). The main expectation regarding the use of ultrasound devices in the diagnosis of temporomandibular joint diseases is the use of this method as a screening test. Magnetic resonance imaging, which is associated with exposure to magnetic fields, is very expensive, not found in most medical facilities, and is impossible in patients with claustrophobia. Computed tomography and cone beam computed tomography do not show soft tissues such as joint disc. Computed tomography scans are not performed more than once or twice a year due to exposure to x-rays. Panoramic radiographs available in many dentist clinics show only very advanced changes in the temporomandibular joint. Accurate diagnosis of temporomandibular diseases is not possible only with clinical examination(1).

--	---

Protocol Information Form for Clinical Research	Doc. Code	Rev. Date/ No:	Page
	Form 3	13.06.2013/İÜDHFKA EK 00	1/6

1. Klatkiewicz, T., et al., Ultrasonography in the Diagnosis of Temporomandibular Disorders: A Meta-Analysis. Med Sci Monit, 2018. 24: p. 812-817.
2. Su, N., et al., Diagnostic value of ultrasonography for the detection of disc displacements in the temporomandibular joint: a systematic review and meta-analysis. Clin Oral Investig, 2018. 22(7): p. 2599-2614.
3. Melis, M., S. Secci, and C. Ceneviz, Use of ultrasonography for the diagnosis of temporomandibular joint disorders: a review. Am J Dent, 2007. 20(2): p. 73-8.

**PURPOSE OF THE RESEARCH** In the literature, there are not many studies on the diagnostic value of the use of ultrasonography in the diagnosis of temporomandibular joint diseases in dentistry. In this study, it is aimed to contribute to the literature in terms of revealing the reliability of the use of ultrasonography in the diagnosis of temporomandibular joint diseases.

**BENEFITS EXPECTED AT THE END OF THE RESEARCH** By revealing the efficacy and reliability of ultrasonography in the diagnosis of temporomandibular joint diseases, to eliminate the disadvantages of MR and other imaging methods.

**RESEARCH METHOD** Functional joint examination and ultrasonographic examination (USG) will be applied to all volunteers who will participate in the research. In the USG application, when the mouth is open and closed, the right and left joint intervals will be measured and a note will be taken. At the same time, right and left masseter muscle thicknesses will be measured separately at free-closing and tight-closing and a grade will be taken for all groups..

Volunteers to participate in the research will be divided into 4 groups.(I,II,III,IV).For volunteers in group 1 with previously taken MR images, USG and MR findings will be compared. In volunteers in group 2, the values obtained using different probes (linear, hockeystick) will be compared. In the third group of volunteers, the values to be obtained by using the USG probe at different angles (horizontal / longitudinal) will be compared. In volunteers in group 4, the megahertz values of the probe are changed and the findings obtained by examining them separately will be compared.

In addition to evaluating 4 groups separately, at the end of the research, USG data applied to all 4 groups will be

Protocol Information Form for Clinical Research	Doc. Code	Rev. Date/ No:	Page
	Form 3	13.06.2013/ÜDHFKA EK 00	2/6

analyzed by comparing all the findings obtained in functional joint examination.

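### The aim is diagnostic, but the plan specifies no target condition, rule for a positive ultrasound, matching MR classification or accuracy measure, so the group 1 comparison as written cannot support a diagnostic conclusion

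*Combined protocol and SAP*

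**What the plan says.** **Aim.** Purpose of the Research speaks of "revealing the reliability of the use of ultrasonography in the diagnosis of temporomandibular joint diseases". The rationale section adds, about screening: "The main expectation regarding the use of ultrasound devices in the diagnosis of temporomandibular joint diseases is the use of this method as a screening" […]. The expected benefit is to overcome the drawbacks of MR and other imaging.

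**USG quantities.** Research Method names two. On the joint: "In the USG application, when the mouth is open and closed, the right and left joint intervals will be measured and a note will be" [made]. On the muscle: "right and left masseter muscle thicknesses will be measured separately at free-closing and tight-closing and a grade will be taken for all groups". The grade has no scale.

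**Comparisons.** "For volunteers in group 1 with previously taken MR images, USG and MR findings will be compared". Neither set of findings is defined. Groups 2, 3 and 4 compare probes, probe angles and probe frequencies. At the end, USG data from all four groups are compared with the functional joint examination.

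**Reference.** The rationale section says: "Magnetic resonance imaging is considered the gold standard in the evaluation of the articular disc as well as soft tissues". It also says that clinical examination alone cannot give an accurate diagnosis.

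**Analysis.** The statistical methods section lists the Chi-Square test for categorical variables, Student's t or Mann Whitney U for continuous ones, and descriptive statistics. The categorical variables are not named. Sensitivity, specificity, ROC analysis, kappa and intraclass correlation do not appear.

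**The concern.** A claim about diagnosis or screening needs a USG result that can be scored right or wrong against a reference, joint by joint. Lengths become such a result only when a target condition, a cut-off and a reference classification are attached to them, and the plan attaches none.

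At stake is the conclusion the protocol wants to draw. A significant or non-significant difference in mean joint interval, or close USG and MR values, would not show whether USG separates diseased from healthy joints. If the categories are settled only after the images have been seen, they can be chosen to suit the result. A call not made at the scan may also not be recoverable later.

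**Working it through.** **1. What the study is sized for.** Sample Information gives f(α,β) = 7.85, SD = 0.05 and a difference of 0.02. The two-sample formula for means gives

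n = 2 × 7.85 × (0.05/0.02)² = 2 × 7.85 × 6.25 = 98.1, or 99 after rounding up, against the stated 100.

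The figure reproduces as the size per group for comparing two means. The variable and unit are not named. The sizing therefore rests on a mean difference, not on accuracy or agreement. (That 100 is then used as the total over four groups is a separate matter.)

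**2. What an accuracy result needs, and what the plan supplies.**

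- *Target condition.* The aim names TMJ diseases as a whole. No specific condition, such as disc displacement, is set as the one to be detected.
- *USG call for each joint.* Joint interval and masseter thickness are named. No cut-off, disc position or positive/negative call is given.
- *Reference call for each joint.* Group 1 has MR images, but no MR categories or reading procedure are given.
- *Accuracy measure.* None is listed.

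**3. What the listed tests would deliver.** They look for differences between groups. The only groups defined are I to IV, which differ by available MR, probe, angle and frequency, not by disease status. Comparing group 1 with another group therefore says nothing about accuracy. Within group 1, a test of mean USG interval against a mean MR value would address average offset, not whether individual joints are classified correctly. A Chi-Square test on some categorical finding would give evidence of association; its p-value is not a sensitivity or specificity.

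**4. Whether the functional examination fills the gap.** It is done in everyone, so it could supply a clinical classification. None is named, however, and the protocol itself says that clinical examination alone is not enough for accurate diagnosis. It cannot serve as the sole reference on the protocol's own terms.

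**The case against.** The strongest reply is that missing specification is not proof of missing data. Group 1 is to compare findings, whereas groups 2 and 3 compare values, so the wording does not confine group 1 to lengths. Functional examination findings will be collected. The statistical section expects categorical variables, with frequencies and percentages. All of this stands. A reader might infer that no diagnosis or disc position will be recorded; the documents show only that none is specified.

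A second reply is that a continuous measurement can be a diagnostic index. This also stands: joint interval could be assessed by ROC analysis against an MR classification. A reader might infer that these measurements can never speak to diagnosis, but the limitation lies in the plan, not in the measurement. Part of the defect is in the analysis section.

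Third, the aim covers TMJ disease generally, and eligibility includes pain in the chewing muscles, so disc position is not the only defensible target and a muscle measurement has a place. In groups 2 to 4, continuous measurements are natural outcomes. The criticism therefore applies mainly to group 1 and to the comparison with functional examination.

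Finally, it is tempting to convert the sample-size inputs into a misclassification rate. The documents do not support this. The inputs have no unit or variable and are not tied to joint width or to diseased versus healthy joints. Sample Information lets both the difference and the SD run from 0.01 to 0.05, so the standardised difference d runs from 0.01/0.05 = 0.2 to 0.05/0.01 = 5. Under normality, AUC = Φ(d/√2) then runs from about 0.56 to above 0.99, which covers almost everything from near-useless to near-perfect.

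**Conclusion.** The concern holds as a gap between aim and specification. None of the four elements needed for a diagnostic accuracy result is stated, and the listed tests do not supply one. As written, the group 1 comparison cannot support a diagnostic or screening conclusion, and the comparison with functional examination does not repair this.

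The verdict does not extend to saying that no diagnostic information will be collected, that joint interval has no diagnostic value, or that groups 2 to 4 have unsuitable outcomes. No numerical size can be given. The verdict rests on the text available for review and assumes that no part of the form not seen defines these elements. The matter should be settled before scanning begins.

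**What to change.** Before the first scan:

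- Name the target condition. Disc displacement on MR is one option.
- Record one USG call per joint at the planned open-mouth and closed-mouth scans, with a category for joints that could not be visualised.
- Read the same categories per joint from the existing group 1 MR images. Make each call without knowledge of the other.
- Make per-joint sensitivity and specificity against MR the main group 1 outcome, with confidence intervals that allow for two joints per patient, and report the number not visualised.
- Add ROC analysis of joint interval against the MR classification.
- Keep joint interval and masseter thickness as secondary measurements in group 1 and as the outcomes for groups 2 to 4.

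If no call can be made, limit the conclusion to measurement of joint interval and muscle thickness.

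**Cost.** One field per joint on the scan form, and some reading time for the MR images, since no MR reading procedure is given. No new scan or patient is needed.

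**Limit.** Not-visualised joints and the unstated size of group 1 will restrict precision. As an illustration, assume an observed sensitivity p = 0.80 and n independent diseased joints. The 95% Wilson interval, with z = 1.96, is

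[p + z²/(2n) ± z√(p(1−p)/n + z²/(4n²))] / (1 + z²/n).

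- n = 12: 52% to 94%
- n = 25: 61% to 91%
- n = 50: 67% to 89%

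If the two joints of a patient tend to be read correctly or incorrectly together, the intervals will be wider. The size of group 1 should therefore be stated along with the new outcome.

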## SAMPLE INFORMATION

How was the number of volunteers to participate in the research determined? Explain	When calculating the sample size of our study, reference values in previous similar studies were taken into consideration. When similar dental studies are examined; ( $\mu_1 - \mu_2$ ) and sd values are seen to range from 0.01 to 0.05 (Odacı E. v.d, 2003). When determining the sample size of the study ( $\alpha=0,05$ , $1-\beta=80\%$ ) $f(\alpha, \beta)=7,85$ , $sd =0,05$ and ( $\mu_1 - \mu_2$ ) = 0,02 when taken, it is seen that the sample size is $n = 100$ . It is planned to include 100 volunteers in our research.
Sampling method	Volunteers will be selected from patients who applied to our clinic and who have complaints of temporomandibular joints.

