**WHICH STATISTICAL METHODS WILL BE EVALUATED**

In our study, SPSS application will be used for statistical analysis.

In evaluating the categorical variables, the Chi-Square test will be used to look for a difference between the groups. Normality control of continuous variables will be done with Kolmogorov-Smirnov test.

Difference evaluations of continuous variables between groups will be made with Student's t test in data with normal distribution. Group comparisons for data that are not suitable for normal distribution will be performed with Mann Whitney U test.

Descriptive statistics will be specified by giving mean, standard deviation, minimum and maximum values of all continuous variables. Frequency distributions and percentages of categorical variables will be specified.

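### Eight ultrasound measurements are compared in four groups and again in a pooled analysis with none named primary, so the single 5% alpha and 80% power do not describe the study's conclusions

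*Combined protocol and SAP*

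**What the plan says.** Under Research Method, the joint is measured in two mouth positions on both sides: "when the mouth is open and closed, the right and left joint intervals will be measured and a note will be taken". The masseter is measured in two closing states on both sides: "right and left masseter muscle thicknesses will be measured separately at free-closing and tight-closing". The masseter measurement is stated to apply to all groups.

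The same section gives each group its own question: USG against earlier MR images (group 1), two probes (group 2), two probe angles (group 3) and different probe frequencies (group 4). A further analysis then sets the USG data of all four groups against the functional joint examination.

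Sample Information gives one alpha (0.05), one power (80%), one standard deviation (0.05) and one difference (0.02). None is attached to a measurement, unit or group. It concludes: "It is planned to include 100 volunteers in our research".

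The statistical methods section says: "Difference evaluations of continuous variables between groups will be made with Student's t test" when data are normal. It names the Mann-Whitney U test otherwise, and chi-square for categorical variables. Nothing in the text available for review names a primary measurement, ranks the comparisons, adjusts for multiplicity or labels any test exploratory.

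**The concern.** Someone following this plan will produce many p-values of equal standing. A result such as an effect of probe type or frequency could then rest on one small p-value among eight or more, with nothing fixed in advance to show whether it was the intended test. The 5% and 80% in the sample-size statement would be read as properties of the study's conclusions, although they are properties of a single comparison that the plan does not identify.

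**Working it through.** **1. What the stated alpha and power cover.** Inputs from Sample Information: multiplier 7.85, SD 0.05, difference 0.02. The multiplier is (1.960 + 0.842)² = 7.85, which is one two-sided 5% test at 80% power. For two independent arms, n per arm = 2 × 7.85 × 0.05² / 0.02² = 98.1. The plan's 100 is therefore reproduced, but as the size of each arm in one two-arm comparison. A paired or one-sample calculation would give 7.85 × 0.05² / 0.02² = 49.1.

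**2. Number of tests** (inferred; the plan gives no count). Measurements per volunteer: 2 positions × 2 sides + 2 closing states × 2 sides = 8.
- All eight compared in every group: 8 × 4 = 32.
- MR supplies only the four joint intervals: 8 × 3 + 4 = 28.
- MR supplies none of the eight: 8 × 3 = 24.

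Pooled comparisons are additional, as are further tests if group 4 uses more than two frequencies.

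**3. Upper figure.** With no true differences and k independent 5% tests, the chance of at least one false positive is 1 − 0.95^k, and 0.05k are expected.

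| k | at least one | expected |
|---|---|---|
| 8 | 33.7% | 0.4 |
| 24 | 70.8% | 1.2 |
| 28 | 76.2% | 1.4 |
| 32 | 80.6% | 1.6 |

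**4. Allowing for correlation.** The eight measurements come from one person, so they are not independent. The documents give neither correlations nor group sizes. The simulation assumes 25 per group, eight equally correlated paired t tests in each group, and independence between groups because the volunteers differ. Across four groups the figure is 1 − (1 − p)⁴, where p is the figure within one group; with three groups the exponent is 3.

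| correlation | one group (8 tests) | four groups (32) | three groups (24) |
|---|---|---|---|
| 0.3 | 30% | 76% | 66% |
| 0.5 | 25% | 69% | 59% |
| 0.8 | 16% | 51% | 41% |

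**5. The tests the plan names.** The group comparisons read as two readings on the same volunteer, but only unpaired tests are listed. An unpaired t test on positively correlated pairs rejects less often than 5%. Simulated with 25 pairs and no true difference:
- Within-pair correlation 0.3: about 2.05% per test, and 1 − 0.9795³² ≈ 49% over 32 independent tests.
- Within-pair correlation 0.5: about 0.7% per test, and 1 − 0.993³² ≈ 20%.

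**6. The pooled comparison.** Here volunteers with and without an examination finding are different people, so an unpaired t test holds its 5%. Assume 100 volunteers and one yes/no finding that splits them evenly. Eight tests then give at least one false positive in about 30%, 25% and 16% of studies at correlations 0.3, 0.5 and 0.8. Three independent findings (assumed), tested on all eight measurements, give about 66%, 58% and 40%.

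**The case against.** A reader might infer that the plan contains at least 32 tests and that a chance finding is therefore more likely than not. The documents do not support that as an unconditional statement, for four reasons:

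- The count of 32 needs MR to supply all eight measurements, including masseter thickness in both closing states, and the protocol does not say that it does. The pooled tests could bring the total back to 32 or more, but only if each measurement is tested there, which is not stated either.
- Across four groups the figure is close to 50% at a correlation of 0.8. With three groups it is 41%.
- Applied as written to same-volunteer pairs, the unpaired tests bring the within-group figures below 50% once the pairs correlate at about 0.3.
- The four groups ask different questions in different people. Treating them as one family is a choice. Within one question the figure is 16–30%.

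All four points stand, and they limit the size of the claim. They do not remove it. The low rejection rate of unpaired tests on paired data comes from a mismatched test, and it disappears once paired tests are used. It gives no protection to the pooled analysis. Even 16% within one question is about three times the stated 5%.

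The Research Design form also appears to mark the study as descriptive, although the table is hard to read. That softens the consequence. But the sample size is built on a hypothesis test and the analysis section prescribes tests of difference, so the form does not make those tests exploratory.

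**Conclusion.** The concern holds in limited form. The plan leads to roughly 24 to 32 unranked group-level tests plus pooled ones, while its error rates belong to one unidentified two-arm difference. With valid 5% tests and no true differences, the chance of at least one false positive is about 16–30% per group question and about 51–76% across four groups that each test all eight measurements. The figure of 81% is a ceiling that needs 32 independent tests. These values rest on assumed correlations of 0.3 to 0.8 and 25 volunteers per group. They would be lower if unpaired tests were applied to same-volunteer pairs, or if group 1 contributed fewer comparisons. The missing primary measurement does not depend on any of these assumptions. This should be corrected, and it can be corrected without changing the design.

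**What to change.** - For each group's comparison, name one primary measurement before any data are seen, for example one joint-interval position with right and left averaged per volunteer.
- Tie the alpha and power statement in Sample Information to that measurement, with its unit, its standard deviation and the number of volunteers in that group.
- Report all other measurements and the pooled comparisons as differences with 95% confidence intervals, labelled exploratory and without significance claims.
- Do not use Holm-adjusted tests for the rest. In a reliability study a stricter threshold makes real disagreement harder to detect. At Holm's first step for 32 tests (0.05/32 = 0.0016), power for the plan's own difference with 100 per arm falls from 80.7% to 36.9%.
- State that a non-significant difference will not be read as agreement.

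Four primary tests at 5% remain, one per question, with 1 − 0.95⁴ = 18.5% across the study if no true differences exist. That is defensible for four separate questions, provided it is stated.

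The cost is protocol wording, with no added volunteers or scans. The small downside is that secondary measurements can no longer be claimed as significant. Tying power to a group's actual size may also show that it falls short of 80%. With 25 pairs, and if 0.05 were the standard deviation of the paired differences, 0.02 / (0.05/√25) = 2.0 and power is Φ(2.0 − 1.96) ≈ 52%.

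### Probe, angle and megahertz are each compared in a separate group although every volunteer is scanned; with an equal split, each question gets about 25 pairs instead of 75 or 100

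*Combined protocol and SAP*

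**What the plan says.** The Research Method section of the combined protocol and SAP starts from a common examination: "Functional joint examination and ultrasonographic examination (USG) will be applied to all volunteers who will participate in the research". It then divides the volunteers into four groups, each with its own question:

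- Group 1: "For volunteers in group 1 with previously taken MR images, USG and MR findings will be compared".
- Group 2: "In volunteers in group 2, the values obtained using different probes (linear, hockeystick) will be compared".
- Group 3: "In the third group of volunteers, the values to be obtained by using the USG probe at different angles (horizontal / longitudinal) will be compared".
- Group 4: "In volunteers in group 4, the megahertz values of the probe are changed and the findings obtained by examining them separately will be compared".

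The four groups are evaluated separately. The one analysis that pools them sets ultrasound against the functional joint examination, so it adds nothing to the technique comparisons.

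Sample Information gives a single total: "It is planned to include 100 volunteers in our research". Group sizes, the way volunteers are allocated to groups, and a reason for keeping the technique questions apart are not given. The statistical methods section lists Student's t test and the Mann-Whitney U test for continuous data and no paired method.

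**The concern.** Changing the probe, the angle or the frequency is something done to one person in one session. If both readings come from the same volunteer, that volunteer can also supply the other two comparisons. Only group 1 has a genuine entry condition, an existing MR image. Confining each technique question to its own group therefore discards most of the pairs that 100 scanned volunteers could provide, and each estimate is less precise than it need be for the same recruitment.

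A second weakness belongs with this one. The plan treats probe, angle and frequency as factors that may each change the reading, but does not say that the other two are held fixed while one is varied. Separate groups do not secure that.

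**Working it through.** **The plan's own figure.** Inputs from Sample Information: difference 0.02, SD 0.05, two-sided multiplier f = 7.85 (alpha 0.05, power 80%).

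2 × 7.85 × 0.05² / 0.02² = 98.1, which agrees with the stated 100. This is the two-sample formula, so 98.1 is the number of readings needed on *each* side of one comparison when the readings are uncorrelated. The one-sample or paired form with an SD of differences of 0.05 gives 7.85 × 0.05² / 0.02² = 49.1, which does not match. I therefore treat 0.05 as the SD of a single reading.

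**Pairs per technique question.** Assuming an equal split: 100 / 4 = 25. If groups 2 to 4 each make all three comparisons: 75. If everyone does: 100.

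**Precision.** The 95% half-width for a mean within-volunteer difference, in units of the SD of the differences, is t(0.975, n−1)/√n:

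- n = 25: 0.413
- n = 75: 0.230
- n = 100: 0.198

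The standard error ratio of the present design is √(100/25) = 2 against 100 pairs and √(75/25) = 1.73 against 75. Neither depends on the correlation between readings.

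**Power for a difference of 0.02.** SD of differences = 0.05 × √(2(1−ρ)), where ρ is the correlation between the two readings of one volunteer. The documents do not give ρ, so a range is shown. Two-sided 5% paired t test, noncentral t:

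| ρ | SD of differences | 25 pairs | 75 pairs | 100 pairs |
|---|---|---|---|---|
| 0 | 0.071 | 27% | 68% | 80% |
| 0.5 | 0.050 | 48% | 93% | 98% |
| 0.7 | 0.039 | 70% | 99% | >99% |
| 0.8 | 0.032 | 86% | >99% | >99% |
| 0.9 | 0.022 | 99% | >99% | >99% |

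If the 25 pairs were analysed as two independent sets of 25, as the listed tests imply, nominal power would be 29%.

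**Readings per volunteer.** Joint interval (open, closed) and masseter thickness (free, tight closing), right and left: 4 × 2 = 8 per setting. At present this is 8 × 2 = 16 in groups 2 to 4 and 8 in group 1. With one alternative for each factor:

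- Both sides throughout: 8 × 4 = 32.
- Reference on both sides, alternatives on one side: 8 + 3 × 4 = 20.

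**Information in the one-sided version.** Let r (0 to 1) be the correlation between the two sides' differences, and s² the variance of one side's difference. Averaging both sides gives variance s²(1+r)/2 per volunteer; one side gives s². Relative to 25 volunteers measured on both sides, the information is (100/25) × (1+r)/2 = 2(1+r), that is 2 to 4 times, with 100 volunteers. With 75 it is (75/25) × (1+r)/2 = 1.5(1+r), or 1.5 to 3 times.

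**The case against.** Five points can be made for the present plan.

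- **The power loss may be small.** Two readings of the same joint in the same person are unlikely to be unrelated, so 27% is the least plausible row. At ρ = 0.8, 25 pairs already exceed 80%, and at 0.9 the loss has gone. This stands: without a value for ρ, only the loss of precision can be asserted.
- **Neither 25 nor pairing is stated.** This also stands. Group sizes are absent, and group 1 depends on who already has MR images. Still, any division that leaves all four groups populated gives each question fewer than 100 volunteers. If different people were meant for the two settings within a group, the present design would be weaker still.
- **A reader might infer that the purpose of groups 2 to 4 is to rank the three factors, and that the split defeats it.** The documents do not support this. The stated purpose is the reliability of ultrasound in diagnosis, and the comparisons are listed as separate questions. Effects from separate groups can also be compared, with a wider standard error, if the groups are comparable.
- **Holding the other factors fixed is a different matter.** True: it could be done within the split design, and using every volunteer does not do it automatically. It has to be written in either way.
- **More scanning has a cost.** With 25 per group, total readings rise from 25 × 8 + 75 × 16 = 1,400 to 2,000 (20 each) or 3,200 (32 each). The rationale section calls ultrasound "less expensive, less time consuming and easy to apply", but that is a comparison with MR, arthrography and CT and does not show that a longer ultrasound session is negligible. Burden could justify separate groups, but the plan does not say so.

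**Conclusion.** The concern holds as a point of efficiency. On the within-volunteer reading and an equal split, each technique comparison has about 25 pairs. Its standard error is twice what 100 pairs measured on both sides would give, or 1.73 times what 75 would give. That follows at any correlation. The effect on power ranges from large (27% against 80% at ρ = 0) to nil (99% or more either way at ρ = 0.9).

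A reader might also infer that using every volunteer restores the stated 80% power for each comparison. That is not unconditional. At ρ = 0 it needs all 100 volunteers, group 1 included, measured on both sides, with 0.05 as the single-reading SD and a paired analysis in place of the listed tests. With groups 2 to 4 only, power at ρ = 0 is 68%. The one-sided version gains less than the full one.

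**What to change.** 1. Name one reference setting of probe, angle and frequency.
2. In every volunteer, or at least in groups 2 to 4, take the reference readings and then each one-factor change (other probe, other angle, other frequency), holding the remaining two factors fixed as far as the equipment allows. The documents give no probe frequencies, so whether the two probes share one must be checked.
3. Randomise the order of settings within the session. The readings include open-mouth and tight-closing positions in patients recruited with joint and chewing-muscle pain, so always taking the reference first would mix setting with fatigue or drift.
4. Analyse each comparison as paired, by paired t test or Wilcoxon signed-rank test with the volunteer as the unit, in place of the unpaired tests now listed. Right and left sides are correlated readings, not extra volunteers.
5. Keep group 1 as the subset that also has MR, and state the group sizes.

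The cost is longer scanning, with no added recruitment. Taking the alternative readings on one randomly chosen side means 20 readings instead of 16 in groups 2 to 4 (and 20 instead of 8 in group 1, if included). Doing both sides means 32. Several frequency values would add more. If session length rules this out, the plan should say so and give the expected precision for each group as it stands.
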